## 4.0 STUDY DESIGN

### 4.1 Overall Design

This is a Phase 2a, single center, double-blind, randomized, placebo-controlled, parallel group study to assess the safety, tolerability, and efficacy of 20 mg per day intranasal OP0201 (10 mg administered BID for a total of 20 doses) as an adjunct therapy to oral antibiotic treatment of AOM in infants and children aged 6 to 24 months (inclusive). Participants will be followed for up to 20 days after study treatment is discontinued. The total duration of study participation for each Participant is up to 30 days, which includes 4 clinic visits: Visit 1: (Day 1) Screening/Enrollment and initiation of the study treatment and oral antibiotics administration; Visit 2: (Day 4 [+2]); Visit 3: (Day 12 [+2]); and Visit 4: (Day 28 [ $\pm 2$ ]) Study Exit. On Day 1 potential Participants' parents/legal guardians in attendance at the study center will be told about the study and those Participants whose parents/legal guardian provide written informed consent will be evaluated for study eligibility. Those who meet all inclusion and no exclusion criteria will be enrolled and randomized (1:1 ratio) to receive a total of 20 intranasal doses (over approximately 10 days) with 20 mg per day OP0201 (10 mg BID) or placebo as an adjunct treatment to standard oral antibiotics (amoxicillin-clavulanate given BID for 20 doses).

Parents/caregivers of the Participants will complete an electronic daily diary on all days when study treatment is given (approximately 10 days) to record BID administration of the oral antibiotic and study treatment, and to record daily AOM-SOS scores.

At each study visit, assessments include a physical examination (including visual examination of the nasopharynx and oropharynx) and measurement of vital signs, pneumatic otoscopy to assess TM of each ear, endoscopic examination with image capture of each ear when possible, and tympanogram (to be performed when possible) of each ear. Adverse events and concomitant medication use will be recorded. At the Day 12 Visit, parents/caregivers will complete the Device Experience Questionnaire. The study assessments are summarized in [Table 3](#).

An unscheduled interim/sick visit may occur for safety purposes or if AOM symptoms have relapsed or worsen. Applicable procedures (eg, physical, otoscopy, tympanometry) will be performed and recorded in the electronic case report form (eCRF).

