### **6.5.1 Excluded Medications**

Participants must abstain from taking antimicrobial therapy within the 3 days (ie, 72 hours) prior to Day 1. Excluded medications/therapy is listed below:

- Any intranasal treatments other than saline rinse.

- Any systemic or locally administered drug containing phenylephrine.

The use of an excluded medication/therapy is a protocol violation and must be recorded in the eCRF.

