## 9.3 Populations for Analyses

Four populations will be considered. The screened population will be all Participants whose parent/legal guardian signs the ICF. Safety data and secondary efficacy endpoints will be analyzed using the safety population defined as all Participants who received at least 1 intranasal spray of study treatment. The intent-to-treat (ITT) population is defined as all randomized Participants and will be used to assess the primary efficacy endpoint family. The per-protocol population is defined as the subset of the ITT population who have no protocol violations affecting the primary efficacy endpoint family and will be used to confirm results from the primary efficacy endpoint family.

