### 9.4.1 Efficacy Analyses

The analysis of the primary efficacy endpoint family will compare the 2 treatment groups (OP0201, placebo) with respect to the proportion of Participants with no bulging of the TM at the Day 4 Visit as well as the proportion of Participants with no MEE at the Day 12 Visit using the ITT population for which Participants with missing data at the Day 4 Visit will be considered as having bulging TM and those with missing data at the Day 12 Visit will be considered as having MEE. A sensitivity analysis will be done that defines the endpoints as no bulging of the TM at the Day 4 Visit and no recurrence of bulging TM throughout the remainder of the study, and no MEE at the Day 12 Visit and no recurrence of MEE throughout the remainder of the study. Sensitivity analyses will also be done using the per-protocol population. Treatment groups will be statistically compared using generalized estimating equations (GEE), if possible, with an alternative method (eg, logistic regression) at each visit as an alternative if GEE convergence cannot be achieved. Randomization stratifiers (daycare attendance [yes, no] and age group [ $\geq 6$  to  $<12$  months,  $\geq 12$  to  $\leq 24$  months]) and degree of TM bulging at baseline will be covariates. Tympanic membrane bulging at baseline will also be evaluated as a potential effect modifier.

The step-up Hochberg procedure will be used to control the familywise Type 1 error. Specifically, the endpoint with the highest p-value will be tested first at the 0.05 significance

level and, if significant, both endpoints will be declared significant; if the endpoint with the highest p-value is not significant at the 0.05 level, the other endpoint will be tested at the 0.025 significance level. A positive treatment effect on efficacy will be concluded if at least 1 of the 2 endpoints in the primary efficacy endpoint family is significant

Descriptive statistics will be provided for the primary efficacy endpoint family by the following sub-groups: age stratum ( $\geq 6$  to  $< 12$  months,  $\geq 12$  to  $\leq 24$  months), race (Caucasian, non-Caucasian), gender (male, female), laterality of disease (unilateral, bilateral), history of recurrent AOM defined as 3 or more episodes in the preceding 6 months or 4 or more episodes over the course of 12 months (yes, no), and daycare attendance stratum defined as exposure to 3 or more children outside of the home for 10 or more hours per week (yes, no).

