3. STUDY DESIGN

This is a Phase 2a, single-center, double-blind, randomized, placebo-controlled, parallel-group study to assess the safety, tolerability, and efficacy of 20 mg per day intranasal OP0201 (10 mg administered twice/day (BID) over 10 days for a total of 20 doses) as an adjunct therapy to oral antibiotic treatment of AOM in infants and children aged 6 to 24 months (inclusive). Subjects will be followed for up to 20 days after study treatment is discontinued. The total duration of study participation for each subject is up to 30 days, which includes 4 clinic visits. An unscheduled interim/sick visit may occur for safety purposes or if AOM symptoms have relapsed or worsened. The Schedule of Activities is in Appendix A.

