7. ANALYSIS POPULATIONS

Screened Population: Subjects whose parent/legal guardian signed the informed consent form.

Confidential Page 12 of 35

Safety Population: Subjects who received at least one intranasal spray of study treatment. Subjects will be summarized and analyzed based on treatment received.

Modified Intent to treat (mITT) Population: Subjects who were randomized excluding the first 3 subjects dosed (subject numbers 1001, 1002 and 1003), as there was a known device malfunction for these subjects. Subjects will be summarized and analyzed based on randomization assignment, regardless of treatment received.

Per Protocol (PP) Population: Subset of the mITT population with no protocol violations that may have affected the primary efficacy endpoint family.

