9.4 Protocol Deviations

A listing of protocol deviations will include protocol version and the category of the deviation (to be determined). Frequency and percentage of subjects in each deviation category will be summarized.

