12.1 Bulging TM

The presence/absence of bulging TM will be evaluated as part of the ear examination (see Section 11.4) done at each study visit; each ear will be evaluated separately.

A listing of bulging TM will be produced separately from the listing of ear examination parameters noted in Section 11.4.

Endpoints

The definition of bulging TM will be presence of 1+, 2+, or 3+ bulging on ear examination. Note: at least mild bulging is an inclusion criterion.

No bulging TM at the Day 4 visit is one of two endpoints in the primary efficacy endpoint family (see Section 13.5). The hypothesis set to be tested is:

Confidential Page 22 of 35

$$\begin{aligned} &H_o \colon P_A = P_P \\ &vs. \\ &H_A \colon P_A \neq P_P \end{aligned}$$

where P_A and P_P are the population proportions for OP0201 and placebo, respectively, for no bulging TM 4 days after the start of a 10-day treatment regimen.

The following sensitivity analyses will be done:

- PP analysis population
- Complete case (ie, mITT subjects who completed the Day 4 visit; see Section 13.3)
- Complete case with the endpoint defined as no bulging TM at the Day 4 visit and no recurrence of bulging TM (see Section 12.7) throughout the remainder of the study, assessed at the Day 28 visit. In this instance, "complete case" is equivalent to mITT subjects who completed the Day 28 visit.

No bulging TM assessed at the Day 12 and Day 28 visits are secondary endpoints.

Summaries and Analyses (see Section 13)

No bulging TM will be summarized and analyzed separately by visit using logistic regression. Summary tables will include frequencies and percentages of no bulging TM for each treatment group by visit and p-values for the differences. Crude rates of no bulging TM by treatment group and visit will be graphically displayed using bar charts.

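### One per-protocol set serves both primary endpoints, so a violation after the Day 4 exam also removes the child from the Day 4 per-protocol sensitivity analysis

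*SAP*

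**What the plan says.** SAP Section 7 defines the PP population once, for the endpoint family: "Subset of the mITT population with no protocol violations that may have affected the primary efficacy endpoint family". Protocol 9.3 does the same, starting from ITT: "The per-protocol population is defined as the subset of the ITT population who have no protocol violations affecting the primary efficacy endpoint family". It adds that this set serves to confirm the primary results.

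The family joins two endpoints assessed about a week apart. The Day 4 exam falls on Study Days 4 to 6 and the Day 12 exam on Days 12 to 14 (SAP 8.7). SAP 12.1 lists "PP analysis population" as a sensitivity analysis for Day 4 bulging, and SAP 12.2 lists the same set for Day 12 effusion. They become Tables 14.2.1.2 and 14.2.2.2 in Appendix B. SAP 9.5 counts one PP population.

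On what counts as a violation, Protocol 6.5.1 is explicit for one item, with no time limit: "The use of an excluded medication/therapy is a protocol violation and must be recorded in the eCRF". The items listed there are intranasal treatments other than saline rinse and drugs containing phenylephrine. SAP 9.4 leaves the deviation categories undecided.

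The PP analysis is supportive. Protocol 9.4.1 says: "Sensitivity analyses will also be done using the per-protocol population".

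**The concern.** A violation between the two exams may affect Day 12 effusion. It then meets the family-level definition, and the child leaves the only PP set there is, including for Day 4. Yet nothing that happens after the Day 4 exam can change what that exam found.

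The reverse path is open: what the exam found may influence later behaviour. A child still bulging may be given other products. A child who has recovered may have doses stopped early. Excluding on such events selects children partly by the outcome being analysed.

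At stake is the reading of Table 14.2.1.2, which Protocol 9.3 treats as confirmation of the primary result. It could look better or worse than the underlying Day 4 effect, and it would rest on fewer children than necessary.

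**Working it through.** **Time at risk.** The regimen is "10 mg administered twice/day (BID) over 10 days for a total of 20 doses". Assume two doses on each of Days 1 to 10. If the exam is on Day 4 before that day's doses, 6 have been given and 14 remain. If it is on Day 6 after the morning dose, 11 have been given and 9 remain. So 9 to 14 of 20 doses, and all days up to the Day 12 exam, fall after the Day 4 exam.

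**The plan's own figure.** The documents give no figure for the PP set. The SAP Section 5 planning inputs are 70 per arm, 10% dropout (63 per arm), 0.40 vs 0.65 at Day 4 and 0.30 vs 0.55 at Day 12. With a two-sided pooled-variance test, power is 0.810 (Day 4) and 0.818 (Day 12) at 0.05, and 0.721 and 0.731 at 0.025. Under Hochberg with independent endpoints:

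- at least one p ≤ 0.025: 0.721 + 0.731 − 0.721 × 0.731 = 0.925
- both p between 0.025 and 0.05: (0.810 − 0.721) × (0.818 − 0.731) = 0.008
- total 0.933, which reproduces the SAP's 93%.

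**Effect of exclusion on Day 4.** Let p be the true proportion without bulging at Day 4. Let vS and vF be the later-violation rates among Day 4 successes and failures. The proportion among retained children is

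p(1 − vS) / [p(1 − vS) + (1 − p)(1 − vF)].

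All values of vS and vF below are assumptions. True proportions are 0.40 vs 0.65, difference 0.250.

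| Later violations (vS / vF) | Placebo | OP0201 | Difference |
|---|---|---|---|
| 10% / 10%, both arms | 0.400 | 0.650 | 0.250 |
| 4% / 12%, both arms | 0.421 | 0.670 | 0.248 |
| 5% / 20%, both arms | 0.442 | 0.688 | 0.246 |
| 5% / 30%, both arms | 0.475 | 0.716 | 0.241 |
| 20% / 5%, both arms | 0.360 | 0.610 | 0.250 |
| 30% / 5%, both arms | 0.329 | 0.578 | 0.248 |
| Placebo 4% / 20%, OP0201 4% / 8% | 0.444 | 0.660 | 0.215 |
| Placebo 4% / 8%, OP0201 4% / 20% | 0.410 | 0.690 | 0.280 |
| Placebo 5% / 5%, OP0201 5% / 20% | 0.400 | 0.688 | 0.288 |
| Placebo 5% / 5%, OP0201 5% / 30% | 0.400 | 0.716 | 0.316 |
| Placebo 5% / 5%, OP0201 20% / 5% | 0.400 | 0.610 | 0.210 |
| Placebo 5% / 5%, OP0201 30% / 5% | 0.400 | 0.578 | 0.178 |

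Differences are taken before rounding. Worked example, row 2: placebo 0.384/(0.384 + 0.528) = 0.4211; OP0201 0.624/(0.624 + 0.308) = 0.6695; difference 0.248. Children lost: placebo 0.4 × 0.04 + 0.6 × 0.12 = 8.8%; OP0201 0.65 × 0.04 + 0.35 × 0.12 = 6.8%.

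**Why the same link in both arms matters little.** Exclusion multiplies the odds of success by (1 − vS)/(1 − vF). If that factor is equal in both arms, the unadjusted odds ratio is unchanged at (0.65/0.35)/(0.40/0.60) = 2.79. Only the absolute difference moves slightly.

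**Under no effect (0.40 in both arms).** With the same link in both arms the difference stays at 0. With the link in OP0201 only (last four rows), it becomes +0.042, +0.075, −0.040 and −0.071. With 63 per arm before exclusion, two-sided rejection at a nominal 5% is then about 7% to 12%.

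**Loss of data alone.** Unrelated 10% exclusion leaves 63 × 0.9 = 56.7 per arm. Day 4 power at 0.05 falls from 81% to 77%, with no bias.

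**The case against.** The strongest reply is that little depends on this table. The success rule applies to the primary mITT analysis. The excluded children stay in that analysis, and those who completed the Day 4 visit also stay in the Day 4 complete-case analysis (Table 14.2.1.3), so a distorted PP result would sit beside two that are not. This stands and keeps the severity low.

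Second, the list of excluding violations is thin. Only excluded-product use is expressly called a violation. Protocol 6.4 has missed doses recorded and dosing resumed, and no document sets a compliance threshold for PP status. A missed Day 12 exam is dealt with as missing data (SAP 13.3). Further antibiotics after treatment failure are provided for in Protocol 4.1 and 6.1.4, so they are not clearly violations. This also stands: the number of children affected is unknown.

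Third, a reader might infer that the Day 4 PP analysis would selectively drop failures and so raise both response rates. The documents do not support a direction. If recovered children are the ones who stop doses early, the rates fall.

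Fourth, an arm-dependent link is hard to motivate in a double-blind trial with products of identical appearance (SAP 6.2). The shifts of 3.0 to 3.5 points in rows 7 and 8 are also less than half a standard error of the Day 4 difference: √[(0.24 + 0.2275)/70] = 0.082. That limits the likely size, but it does not justify the rule.

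Finally, the programmer might apply PP status endpoint by endpoint. That would be sensible, but neither document says so.

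**Conclusion.** The point holds as a defect in a supportive analysis. As written, a qualifying violation after the Day 4 exam removes a child from Table 14.2.1.2, although it cannot have affected the Day 4 result.

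Two consequences follow directly from the wording: valid Day 4 data are lost from that table, and the table is conditioned on later events. Bias in the treatment difference is conditional. In the scenarios run, the same link in both arms moves the arm rates by about 2 to 7.5 points in either direction, but the difference by about 1 point or less. A link that differs by arm moves the difference by roughly 3 to 7 points (3.0 to 7.5), again in either direction. Every one of these sizes rests on assumed violation rates.

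A reader might infer that the trial's efficacy conclusion is at risk. It is not: the Hochberg test on the mITT population does not use the PP set. Severity is low.

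**What to change.** In SAP Section 7, replace the single PP population with two flags:

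- **PP-Day 4:** mITT subjects with no violation, up to the Day 4 exam, that may have affected Day 4 bulging. Use it in SAP 12.1 and Table 14.2.1.2.
- **PP-Day 12:** mITT subjects with no violation, up to the Day 12 exam, that may have affected Day 12 effusion. Use it in SAP 12.2 and Table 14.2.2.2.

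Assign both flags before unblinding. SAP 15.1 already requires deviations to be identified and the database locked before the final analysis, but it does not mention PP status. Report both sets under SAP 9.5, and add a line to SAP Section 16, since Protocol 9.3 has one set.

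This matches the SAP's complete-case sets, which are already tied to the Day 4 and Day 12 visits separately. It removes this source of bias from the Day 4 table entirely. The cost is one extra flag and a few lines of text. The two PP tables may have different denominators, which a footnote can explain. Trial conduct does not change.

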8. REPORTING AND ANALYSIS CONVENTIONS

8.1 Programming Environment

SAS® version 9.4 or higher (SAS Institute, Cary, North Carolina) will be used for statistical analyses and the production of tables, figures, and listings (TFLs).

8.2 Reporting Conventions

Tables of contents for TFLs to be produced are shown in Appendix B. Mock-up TFLs to be produced are provided in separate documents from the SAP. Sponsor approval of mock-up TFLs is included with Sponsor approval of the SAP. Final TFLs will be appended to the final CSR. The following reporting conventions will be followed:

- Font size is to be no smaller than 9pt.
- Titles and footnotes must appear on every page of the TFL.
- Treatment group names and order in tables and figures will be Placebo, OP0201 (20 mg). Some tables and figures may also display All Subjects as a third grouping.
- Tables and figures will present summaries/analyses by study time point or analysis visit window, as appropriate.
- Table column headers and figure legends will include subgroup sample sizes ("N = xx"). Sample sizes reported as part of descriptive statistics ("n") will be the number of non-missing observations.
- Listings will be produced for all study population, safety, and efficacy data collected, either on the electronic case report form (eCRF) or through third-party vendors, and will be ordered by unique subject identifier, parameter, date, data collection time if applicable, nominal study visit, and analysis visit window if applicable (see Section 8.7). Listings will also include site identifier.

8.3 General Analysis Conventions

Categorical variables will be summarized using frequencies and percentages. Percentages will be reported to one decimal place. Unless otherwise noted in Section 12, categorical variables will be analyzed using chi square tests of association (or Fisher's exact test if any contingency table cell has less than 5 observations) or logistic regression to adjust for covariates.

Confidential Page 13 of 35

Continuous variables will be summarized using descriptive statistics (e.g., n, mean, standard deviation (SD), least-squares (LS) mean with standard error (SE), distribution percentiles, range). The number of decimal places for minimums and maximums will be the same as the original data. The number of decimal places for means, medians, and interquartile ranges will be the same as the original data plus one. The number of decimal places for measures of variance will be the same as the original data plus two. Unless otherwise noted in Section 12, continuous variables will be analyzed using t-tests, general linear models to adjust for covariates, or non-parametric alternatives.

Data with qualifiers (e.g., "<") will be listed with but summarized without the qualifier.

P-values will be presented in summary tables to three decimal places. P-values < 0.001 will be presented as "< 0.001."

Statistical tests will be two-sided with 0.05 significance levels unless otherwise noted.

8.4 Subgroups

Summary statistics for the primary efficacy endpoint family will be provided for the following subgroups:

- Male, female
- White, non-white
- Unilateral, bilateral disease at baseline
- History, no history of recurrent AOM, defined as 3 or more episodes in the preceding 6 months or 4 or more episodes over the course of 12 months
- Age stratum (\geq 6 to <12 months, \geq 12 to \leq 24 months)
- Daycare attendance stratum (exposed, not exposed to 3 or more children outside of the home for 10 or more hours per week)
- Study site

8.5 Missing Data

Listings will present data as reported. Missing or partially missing dates that are required for date-dependent definitions (e.g., TEAEs, concomitant medications) will be assumed to be the most conservative date possible. For example, an adverse event (AE) with a completely missing start date will be considered treatment-emergent. Missing observations will not be imputed for summaries. Handling of missing observations for statistical inference is described in Section 13.4.

8.6 Study Period and Time Point Definitions

Screening: Day 1 up to dosing.

Confidential Page 14 of 35

Baseline Observation: for a given parameter for a given randomized subject, the last observed value before the first dose of study treatment or planned first dose of study treatment if not dosed.

Study Day 1: for a given randomized subject, the day of actual first dose of study treatment or planned first dose of study treatment if not dosed.

Study Day:

- Study day = date of assessment date of dosing + 1, for assessments on or after first dose
- Study day = date of assessment date of dosing, for assessments before first dose

Study Time: time of assessment – time of first dose

Duration:

- Duration in days = end date start date + 1
- Duration in minutes = end time start time

(Nominal Visit) Analysis Time Point: analysis based on data collected at the (nominal visit) time point, where nominal visits are as shown below in Section 8.7.

End of Study (EOS), Subject-Level: the date of completion of the last planned study visit or date of discontinuation for any reason.

EOS, Study-Level: the date when all randomized subjects have reached Subject-Level EOS.

8.7 Visit Windows

Visit windows are based on Study Day. Observations will be assigned to an analysis window according to the tables below. Observations that cannot be assigned to an analysis window based on the tables below will be excluded from summaries and analyses (but will still be listed). For subjects not dosed, planned date of first dose will be used in Study Day calculations, if necessary.

For otoscopy and tympanogram parameters:

Nominal Visit	Target Study Day	Min Study Day Per Protocol	Max Study Day Per Protocol	Min Study Day for Analyses	Max Study Day for Analyses
Visit 1 (Day 1 Pre-Dose)	1 (pre-dose)	1	1 (pre-dose)	N/A	1 (pre-dose)
30 Minutes Post-Dose	1 (post-dose)	1 (post-dose)	1 (post-dose)	1 (post-dose)	1 (post-dose)
Visit 2 (Day 4)	4	4	6	4	6
Visit 3 (Day 12)	12	12	14	12	14
Visit 4 (Day 28)	28	26	30	26	30

N/A, not applicable

Confidential Page 15 of 35

Nominal Visit	Target Study Day	Min Study Day Per Protocol	Max Study Day Per Protocol	Min Study Day for Analyses	Max Study Day for Analyses
Visit 1 (Day 1)	1 (pre-dose)	1	1 (pre-dose)	N/A	1 (pre-dose)
Visit 2 (Day 4)	4	4	6	4	6
Visit 3 (Day 12)	12	12	14	12	14
Visit 4 (Day 28)	28	26	30	26	30

N/A, not applicable

For AOM-SOS score collected by diary:

Nominal Visit	Target Study Day	Min Study Day Per Protocol	Max Study Day Per Protocol	Min Study Day for Analyses	Max Study Day for Analyses
Visit 1 (Day 1)	1 (pre-dose)	1	1 (pre-dose)	N/A	1 (pre-dose)
Diary Day x, x=2-10	X	X	X	X	X

N/A, not applicable

If multiple valid, non-missing observations exist within a given window, the observation to be used will be:

- 1. the observation closest to the target study day of the nominal visit in question, or
- 2. the latest observation if the multiple observations are equidistant from the target study day of the nominal visit, or
- 3. the average (arithmetic or geometric, as appropriate) of the observations if the multiple observations have the same actual time point.

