- c Otoscopy and tympanometry (when possible) to be performed prior to the first dose of the study treatment on Day 1. When possible, otoscopy and tympanometry to be performed 30 minutes following administration of the first dose of the study treatment on Day 1. Trained otoscopists who have undergone comprehensive educational program (enhancing proficiency in otitis media) for training in the diagnosis of AOM will perform the otoscopy assessments. This training includes training on cerumen removal, which is required (as needed) prior to performing pneumatic otoscopy or tympanogram.
- d Train parent/caregiver on nasal saline rinse and/or nasal suction on Day 1 and remind parent/caregiver of rinse and/or suction during the study treatment period, as needed.
- e Safety observation for 30 minutes following administration of the first dose of study treatment.
- f If a Participant exits the study prior to the Day 28 Study Exit visit, all Day 28 final measurements should be performed and recorded on the appropriate eCRF.
- g Device Experience Questionnaire should only be completed for all Early Discontinuation Participants if they exit prior to Day 12 and did NOT complete the questionnaire.

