
 
• Any clinically significant abnormal laboratory findings or other abnormal safety assessments which are associated with the underlying disease, unless judged by the Investigator to be more severe than expected for the Participant’s condition.
 
• The disease/disorder being studied or expected progression, signs, or symptoms of the disease/disorder being studied, unless more severe than expected for the Participant’s condition.
 
• Medical or surgical procedure (eg, endoscopy, appendectomy): the condition that leads to the procedure is the AE.
 
• Situations in which an untoward medical occurrence did not occur (social and/or convenience admission to a hospital).
 
• Anticipated day-to-day fluctuations of pre-existing disease(s) or condition(s) present or detected at the start of the study that do not worsen.
 

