11.4 Ear Examination

Examination of each ear will be done at each study visit. Summaries, by ear and visit, will be done for: TM findings (intact, perforated,), color (gray, pink, pale yellow, white, amber, blue), translucency (translucent, semi-opaque, opaque), mobility (none, 1+, 2+, 3+, 4+), air fluid interface (yes, no), otalgia (yes, no), distinct erythema (yes, no), position of the TM (neutral, retracted, 1+ bulging, 2+ bulging, 3+ bulging), otorrhea (no, serous, purulent), and diagnosis (no effusion, OME, AOM).

Confidential Page 21 of 35

Shift tables will summarize changes from baseline in normal/abnormal status, where "abnormal" will be limited to "definitely abnormal" defined as follows:

• TM findings: perforated

• Color: pale yellow, white, amber, blue

• Translucency: semi-opaque or opaque

• Mobility: none

• Air fluid interface: yes

• Otalgia: yes

• Distinct erythema: yes

• Position of TM: retracted, 1+ bulging, 2+ bulging, 3+ bulging

• Otorrhea: serous, purulent

Diagnosis: AOM, OME

Parameters will be summarized within treatment group for (a) first or only affected ear and (b) second or non-affected ear. Since either one ear or both ears can have AOM at baseline, this approach will allow descriptive comparisons between OP0201 and placebo treatment groups on number of affected ears (ie, one or both ears) and shifts from baseline, by visit, for both affected and non-affected ears at baseline.

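### Early-exit and sick-visit examinations outside the SAP 8.7 windows can be left out of the safety shift tables and appear only in listings

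*SAP*

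**What the plan says.** SAP 8.7 rests on the rule "Visit windows are based on Study Day" and gives tables of day limits. For otoscopy and tympanometry after Day 1, the analysis limits are Days 4–6, 12–14 and 26–30, the same as the protocol's visit windows. A second table has the same limits, but its heading is missing from the text extracted from the PDF. No table has a row for early discontinuation or for an unscheduled visit. The rule for data that fit no window is: "Observations that cannot be assigned to an analysis window based on the tables below will be excluded from summaries and analyses". A bracketed clause adds that such data stay in the listings. If several observations fall in one window, the one closest to the target day is used, and the later one if two are equally close.

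The protocol deliberately collects examinations on other days. Footnote f of Table 3 says: "If a Participant exits the study prior to the Day 28 Study Exit visit, all Day 28 final measurements should be performed and recorded". Section 4.1 says: "An unscheduled interim/sick visit may occur for safety purposes or if AOM symptoms have relapsed or worsen". The physical examination and otoscopy done at such a visit go into the eCRF.

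Shifts from baseline in vital signs, physical examination and tympanic membrane (TM) examination are primary safety endpoints (Protocol Section 3; SAP 4.2.1). Protocol 9.4.2 plans the vital-sign, physical and nose/throat shifts by visit. For ears, SAP 11.4 says "Shift tables will summarize changes from baseline in normal/abnormal status". Appendix B lists shift tables for the physical (14.3.9.2.2), ear (14.3.9.3.2) and nose/throat (14.3.9.4.2) examinations. No title there mentions a worst, last or unscheduled value.

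**The concern.** The examinations left out are probably not a random sample. Under Protocol 4.1, a parent's report of worsening, or of symptoms possibly due to study treatment, triggers an interim evaluation, and some children leave early because of a problem. If a child is examined at exit on Day 8, that examination enters no by-visit row. If otorrhea is seen at a Day 8 sick visit and has cleared by Day 12, the Day 4 and Day 12 rows can both be normal.

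Safety and tolerability are primary objectives, and the protocol reports only one child previously exposed to the active ingredients by the intranasal route. The shift tables by arm could therefore show fewer abnormalities than were recorded. The SAP does relax the window once, for the Day 28 visit in the AOM recurrence endpoint (SAP 12.7). That is an efficacy endpoint, and no similar exception covers the safety examinations.

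**Working it through.** The plan gives no figure for this point, so there is none to reproduce. The check counts days and applies the selection rule.

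**Days covered (SAP 8.7).**
- Days 2–30 are 29 days. The windows hold 3 + 3 + 5 = 11 of them, so 29 − 11 = 18 (18/29 = 62%) lie outside: Days 2–3, 7–11 and 15–25.
- Days 2–10, the diary days after Day 1, are 9 days. Only Days 4–6 are covered, so 6 of 9 lie outside.
- An exit before the Day 28 window opens falls on Days 2–25, which are 24 days. Six are covered, so 18/24 = 75% lie outside.

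These are calendar counts, not rates of lost examinations, because the scheduled visits are planned inside the windows.

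**Children with an exit examination at risk.** Inputs are 140 randomized and dropout of 10% (SAP 5) or 12% (Protocol 9.2).
- 140 × 0.10 = 14, and 140 × 0.12 = 16.8, about 17.
- Illustration, assuming that every dropout has an exit examination and that exit days are uniform over Days 2–25: 14 × 0.75 = 10.5, and 16.8 × 0.75 = 12.6.
- The documents give neither exit timing nor attendance at exit visits, so the range is 0 to all 14–17. They give no sick-visit rate either.

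**Selection inside a window.** Take a scheduled examination on Day 4 and a sick visit on Day 6. The distances from target are 0 and 2 days, so Day 4 is kept whatever Day 6 showed. In the Day 4 and Day 12 windows the target is the first day, so when examinations fall on different days the earlier one always wins. The rule can also favor the sick visit: if that is on Day 4 and the scheduled visit is on Day 6, the sick visit is kept. The rule takes no account of severity.

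**Other routes into a table.** Protocol 7.0 asks for new findings of clinical relevance to be recorded as AEs, and the SAP 11.1 tables are not tied to visit windows. Protocol Appendix 3, however, lists among events that are not AEs "The disease/disorder being studied or expected progression, signs, or symptoms of the disease/disorder being studied", with an exception for findings more severe than expected in that child. An off-window ear finding that the investigator regards as ordinary otitis can therefore be in neither the AE tables nor the shift tables. A clinically relevant nasal injury would be in the AE tables.

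**The case against.** The case for leaving the plan alone has substance.

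- **Nothing is discarded.** Listings 16.2.9.1 to 16.2.9.5 show vital signs, physical, ear, nose and throat data for the Safety Population. This stands, but a listing gives no count by arm.
- **AE reporting is the main route for harm.** It runs from consent to end of study, and the criteria for stopping the study (Protocol 5.4.1) rest on AEs. This stands and narrows the gap considerably.
- **The reach beyond otoscopy is inferred.** The second window table may cover all remaining parameters or only the in-clinic AOM-SOS score. In the latter case the effect on physical, nose/throat and vital-sign data is unclear.
- **Exit examinations might be filed under Visit 4.** The schedule puts early discontinuation in that column, and SAP 8.2 allows presentation by time point or by window. This is an open reading, but 8.7 assigns by study day and the SAP does not settle the conflict. Sick visits have no nominal visit at all.
- **The table shells are separate documents.** A row of the kind proposed could already be in them. Appendix B gives titles only.
- **By-visit shifts follow the protocol, and a worst-value ear row could mislead.** SAP 11.4 counts any bulging, otalgia or OME as abnormal, so an unrestricted row would mostly show the disease under study. This stands and shapes the fix.

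A reader might infer that safety data are lost, or that harm in these children escapes all reporting. The listing clause and the AE tables rule that out. A reader might also infer that the omitted examinations are those most likely to show harm. That is plausible for some, but many sick visits will be for AOM itself and the documents give no rates.

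**Conclusion.** The point holds in a limited form. As written, SAP 8.7 keeps off-window otoscopy out of the summaries and shift tables, and apparently the physical, nose/throat and vital-sign examinations too. Early-exit and safety sick-visit examinations can therefore be absent from tables that serve a primary safety endpoint. Inside a window, a worse examination can give way to one nearer the target day. The remaining gap is abnormal findings at unused examinations that are not also reported as AEs, such as ear signs judged to be expected.

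Up to 14–17 of 140 children could have an exit examination affected, with a range of 0 to all of these. That figure is a ceiling under the plan's own dropout assumptions and should not be read as an expected count: children lost to follow-up may have no exit examination, and an exit inside a window may be kept. Sick visits would add to it by an unknown number. How many abnormalities would be hidden cannot be determined from the documents. The change is worth making before database lock because it costs little; the gap does not undermine the safety evaluation as a whole.

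**What to change.** 1. Keep the by-visit rows. Add one row, *worst post-baseline, any visit*, to Tables 14.3.9.2.2 (physical), 14.3.9.4.2 (nose and throat) and 14.3.9.3.2 (ear), using all scheduled, sick-visit and early-exit examinations whatever the study day.
2. For ears, limit the row to perforation, otorrhea and ears unaffected at baseline, where the disease under study does not dominate. Protocol 5.1 requires both membranes to be intact at entry, so any perforation is new.
3. State in SAP 8.7 that neither the window exclusion nor the closest-to-target choice applies to this row.
4. State in SAP 8.7 which visit, if any, an early-exit examination is assigned to in the by-visit tables, and which parameters the second window table covers.
5. Highest and lowest post-baseline vital signs in Table 14.3.9.1 are optional.

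The cost is SAP wording and a little table programming. The data are already collected, and the change does not touch conduct, the efficacy analyses or the type 1 error. The drawback is that a child with more sick visits has more chances of an abnormal result, so the row should be descriptive only, preferably shown with the number of examinations per child by arm.
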